**Table 5 - Analyses of adverse events**

Type of AE	MedDRA levels
All TEAE	Primary SOC, and PT
TEAE related to SAR442720 as per Investigator's judgment	Primary SOC and PT
Treatment emergent SAE	Primary SOC and PT
Treatment emergent SAE related to SAR442720 as per Investigator's judgment	Primary SOC and PT
Treatment emergent SAE related to pembrolizumab as per Investigator's judgment	Primary SOC and PT
Treatment emergent SAE related to adagrasib as per Investigator's judgment	Primary SOC and PT
TEAE leading to permanent full intervention discontinuation	Primary SOC and PT
TEAE leading to permanent discontinuation of SAR442720	Primary SOC and PT
TEAE leading to permanent discontinuation of pembrolizumab	Primary SOC and PT
TEAE leading to permanent discontinuation of adagrasib	Primary SOC and PT
TEAE leading to death	Primary SOC and PT
TEAE leading to dose modification (including dose delay, dose reduction and dose omission) of SAR442720	Primary SOC and PT

### **Analysis of deaths**

The deaths will be summarized by observation period ie, number (%) of deaths during the on-treatment period and number (%) of deaths during post-treatment period.

### **Analysis of adverse events of special interest (AESIs)**

Adverse events of special interest (AESIs) in Section 8.3.7 of protocol amendment 4 will be selected for analyses as indicated from CRF. Number (and percentage) of participants experiencing at least one event will be provided for each event of interest. Tables will be sorted as indicated in [Table 4](#).

## **4.4 EFFICACY ENDPOINT(S)**

Efficacy endpoints involved in this study are summarized in the following table ([Table 6](#)).

**Table 6 - Summary of efficacy endpoints**

Efficacy Endpoint	Part-1/3A	Part-2/3B	Part-4
ORR per RECIST 1.1	Secondary	Primary	Secondary
DoR	Secondary	Secondary	Secondary
PFS	NA	Secondary	NA
TTR	NA	Secondary	NA
CBR	NA	Secondary	NA
OS	NA	Exploratory	NA
ORR per iRECIST	NA	Exploratory	NA

The Best Overall Response (BOR) by RECIST 1.1 will be summarized. The Objective Response Rate (ORR) by RECIST 1.1 is calculated as the proportion of participants with BOR as Complete Response (CR) or Partial Response (PR). The 90% two-sided confidence interval for ORR will be computed using the Clopper-Pearson method.

The primary analysis using the Objective Response Rate (ORR) is performed when all participants have at least 2 post baseline tumor assessments with response durability demonstrated or discontinued study treatment (whichever occurs first). ORR is defined as proportion of participants who have confirmed complete response (CR) or partial response (PR) determined by investigator per RECIST v1.1. The 90% CI is estimated using Clopper Pearson method.

The BOR of CR or PR needs to be confirmed by a subsequent assessment. BOR per RECIST 1.1 will be summarized. Waterfall plot will be generated for the best change from baseline for target lesions for each participant.

Duration of response (DoR) according to RECIST v1.1 will be summarized. The DoR will be defined as the time interval from the date of the first occurrence of CR or PR that is subsequently confirmed (eg, in case of a patient who has four assessments as PR SD PR PR, the second PR date will be used for the calculation) to the date of the first documentation of disease progression or death due to disease progression, whichever occurs first. Participants who are still alive and free from progression at the time of data cutoff date, are lost to follow-up, have discontinued from the study, or who have initiated subsequent anticancer therapy will be censored at the last adequate tumor assessment. For participants who achieve CR or PR, the Kaplan-Meier curve will be generated. The detailed censoring rules are listed in [Table 7](#) below. DoR will be analyzed for responders using Kaplan-Meier methods and following estimates will be provided:

- Kaplan-Meier estimates of the 25th, 50th and 75th percentiles and their associated 90% CIs will be provided. The 90% CIs will be constructed using a log-log transformation of the survival function and the methods of Brookmeyer and Crowley.
- Number of patients at risk as well as the probabilities of being event-free at least 2, 4, 6, 8, 10 and 12 months with 90% CIs will be estimated using the Kaplan-Meier method and a log-log approach based on a normal approximation following the Greenwood's formula.
- Kaplan-Meier curves will be plotted. These plots will include the number of patients at risk at key time points.

In addition, number (and percentage) of events and patients censored will be presented with type of events and reason of censoring.

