7 DISCONTINUATION OF STUDY INTERVENTION AND PARTICIPANT DISCONTINUATION/WITHDRAWAL

7.1 DISCONTINUATION OF STUDY INTERVENTION

7.1.1 Definitive discontinuation

In rare instances, it may be necessary for a participant to permanently discontinue (definitive discontinuation) study intervention. If study intervention is definitively discontinued, the participant will remain in the study to be evaluated for 30 days. See the schedule of activities (SoA; [Section 1.3](#)) for data to be collected at the time of discontinuation of study intervention and follow-up and for any further evaluations that need to be completed.

If a clinically significant finding is identified (including, but not limited to changes from baseline in QTcF) after enrollment, the Investigator or qualified designee will determine if the participant can continue in the study and if any change in participant management is needed. This review of the ECG printed at the time of collection must be documented. Any new clinically relevant finding should be reported as an AE.

Participants may stop study therapy yet continue to be monitored in the study under the following circumstances:

- A participant who experiences a Grade 4 AE, including those that meet the criteria of a DLT (ie, during Cycle 1), but is deemed by the investigator not to meet the criteria for withdrawal from the study (see below).
- Prolonged QTcF >450 msec OR change from baseline of QTcF >50 msec and that does not resolve after excluding other causes.

A participant must be discontinued from protocol prescribed therapy and removed from the study if any of the following apply:

- Documented disease progression based on RECIST v1.1
 - In certain circumstances (eg, an isolated site of progression with responses at other sites that may be amenable to localized radiotherapy), participants may be allowed to continue therapy during and after radiation with approval from sponsor Medical Monitor.
- Significant AEs leading to discontinuation of study medications
- Death
- Participant's request to withdraw from study treatment
- Ineligibility
- Unwillingness or inability to comply with study requirements
- Initiation of alternative anticancer therapy

- Investigator's decision
 - Clinical need for concomitant or other ancillary therapy that is not permitted in the study
 - Unrelated intercurrent illness that, in the judgment of the investigator, will affect assessments of clinical status to a significant degree

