7.2 PARTICIPANT DISCONTINUATION/WITHDRAWAL FROM THE STUDY

A participant may withdraw from the study at any time at his/her own request, or may be withdrawn at any time at the discretion of the Investigator for safety, behavioral, compliance, or administrative reasons. This is expected to be uncommon.

A participant may be withdrawn from the study for any of the following reasons:

- Participant's withdrawal of consent for participation in the study
- Sponsor's decision to terminate the study
- Participant is lost to follow up
- Death

If study discontinuation occurs at the same time as treatment discontinuation, every effort should be made to complete the safety follow up or EOT visit, within 30 days after the last treatment dose. See SoA for data to be collected at the time of study discontinuation and follow-up and for any further evaluations that need to be completed. Participants who do not withdraw consent will also undergo a long term follow up for survival (SoA in [Section 1.3](#)).

The participant will be permanently discontinued both from the study intervention and from the study at that time.

If the participant withdraws consent for disclosure of future information, the Sponsor may retain and continue to use any data collected before such a withdrawal of consent.

If a participant withdraws from the study, he/she may request destruction of any samples taken and not tested, and the Investigator must document this in the site study records.

If participants no longer wish to take the IMP, they will be encouraged to remain in the study.

The Investigators should discuss with them key visits to attend. The value of all their study data collected during their continued involvement will be emphasized as important to the public health value of the study.

Participants who withdraw from the study intervention should be explicitly asked about the contribution of possible AEs to their decision, and any AE information elicited must be documented.

All study withdrawals should be recorded by the Investigator in the appropriate screens of the e-CRF and in the participant's medical records. In the medical record, at least the date of the withdrawal and the reason should be documented.

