## Part-2

	Objectives	Endpoints
Primary	
 
To determine the antitumor activity of SAR442720 in combination with pembrolizumab
 
	
 
Objective response rate defined as the proportion of participants who have a confirmed complete response (CR) or partial response (PR) determined by investigator per RECIST v1.1
 

Secondary	
 
To assess the safety profile of SAR442720 in combination with pembrolizumab
 
To assess other indicators of antitumor activity
 
To assess the PK of SAR442720 in combination with pembrolizumab, and to assess the PK of pembrolizumab in combination with SAR442720
 
	
 
Incidence of TEAEs, SAEs, laboratory abnormalities according to National Cancer Institute Common Terminology Criteria for Adverse Events (NCI CTCAE) V5.0
 
Time to response (TTR) defined as the time from the first administration of investigational medicinal product (IMP) to the first documented evidence of PR or CR determined by investigator per RECIST v1.1 (for NSCLC)
 
DoR, defined as the time from first documented evidence of CR or PR until progressive disease (PD) determined by investigator per RECIST v1.1 or death from any cause, whichever occurs first
 
Clinical benefit rate (CBR) including confirmed CR or PR at any time or stable disease (SD) of at least 6 months determined by investigator per RECIST v1.1
 
Progression free survival (PFS), defined as the time from the date of first IMP administration to the date of the first documented disease progression determined by investigator as per RECIST v1.1 or death due to any cause, whichever occurs first
 
Plasma concentrations of SAR442720
 
Serum concentration of pembrolizumab
 

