### Part-3B

	Objectives	Endpoints
Primary		
	
 
To determine the antitumor activity of SAR442720 in combination with adagrasib in participants with NSCLC and KRASG12C mutations
 
	
 
Objective response rate defined as the proportion of participants who have a confirmed CR or PR determined by investigator per RECIST v1.1
 

Secondary		
	
 
To assess the safety profile of SAR442720 when combined with adagrasib in participants with NSCLC and KRASG12C mutations
 
To assess other indicators of antitumor activity
 
	
 
Incidence of TEAEs, SAEs, laboratory abnormalities according to NCI CTCAE V5.0
 
TTR defined as the time from the first administration of investigational medicinal product (IMP) to the first documented evidence of PR or CR determined by investigator per RECIST 1.1 (for NSCLC)
 
DoR, defined as the time from first documented evidence of CR or PR until progressive disease (PD) determined by investigator per RECIST 1.1 or death from any cause, whichever occurs first
 
CBR including confirmed CR or PR at any time or SD of at least 6 months (determined by investigator per RECIST v1.1)
 
PFS, defined as the time from the date of first IMP administration to the date of the first documented disease progression determined by investigator as per RECIST v1.1 or death due to any cause, whichever occurs first
 
Plasma concentrations of SAR442720 and adagrasib
 

	
 
To assess the PK of SAR442720 in combination with adagrasib, and to assess the PK of adagrasib in combination with SAR442720
 
	

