**Table 7 - DoR analysis - Event and censoring rules**

Situation	Date of outcome	Outcome	Category
Ongoing and no documented progression	Date of the last evaluable tumor assessment documenting no progression	Censored	Ongoing without progression
Documented progression (or Death) at or between scheduled visits	Date of progression (or Date of death)	Event	Documented progression (or Death without documented progression)
Documented progression (or Death) occurring after two or more non-evaluable tumor assessment a	Date of the last evaluable tumor assessment documenting no progression	Censored	Event occurred after two or more missed tumor assessment
Initiation of further anti-cancer therapy	Date of the last evaluable tumor assessment before start date of further anti-cancer therapy	Censored	Initiation of further anti-cancer therapy

a An event occurring at least 19 weeks (excluded) after the last evaluable tumor assessment

Progression Free Survival (PFS) per RECIST v1.1 is defined as the time from the date of the first IMP administration of to the first documentation of definitive disease progression or death due to any cause, whichever occurs first. Participants who are still alive and free from progression at the time of data cutoff date, are lost to follow-up, have discontinued from the study, or who have initiated subsequent anticancer therapy will be censored at the last adequate tumor assessment. The detailed censoring rules are listed in the [Table 8](#) below. PFS will be analyzed using Kaplan-Meier methods and following estimates will be provided:

- Kaplan-Meier estimates of the 25th, 50th and 75th percentiles and their associated 90% CIs will be provided. The 90% CIs will be constructed using a log-log transformation of the survival function and the methods of Brookmeyer and Crowley.
- Number of patients at risk as well as the probabilities of being event-free at least 2, 4, 6, 8, 10 and 12 months with 90% CIs will be estimated using the Kaplan-Meier method and a log-log approach based on a normal approximation following the Greenwood's formula.
- Kaplan-Meier curves will be plotted. These plots will include the number of patients at risk at key time points.

In addition, number (%) of events and patients censored will be presented with type of events and reason of censoring.

[figure not shown]

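### SAP 4.4 ends duration of response at progression-related death only, against the protocol and the SAP's own tables, and Tables 7 and 8 leave two event-or-censor conflicts open

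*SAP*

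**What the plan says.** **DoR.** SAP 4.4 defines the interval as running from the first confirmed response "to the date of the first documentation of disease progression or death due to disease progression, whichever occurs first". The same paragraph then refers onward: "The detailed censoring rules are listed in" Table 7. That table classes its event row as "Documented progression (or Death without documented progression", with no limit on the cause of death. SAP Table 2 ends DoR for Part-2 "until progressive disease (PD) determined by investigator per RECIST v1.1 or death from any cause, whichever occurs first", and its Part-3B entry agrees. Protocol 9.4.2 and protocol Table 12 also count any death. SAP Appendix 2 lists no change to the protocol-planned analyses.

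**PFS.** The definition in SAP 4.4 counts any death, as the protocol does. Table 8 censors at first dose a participant with no baseline scan or no evaluable post-baseline scan. A separate row makes a death at or between scheduled visits an event.

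**Missed scans.** Tables 7 and 8 censor an event that follows two or more non-evaluable assessments. Footnote a sets this at more than 19 weeks after the last evaluable scan, for every part.

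**Scan schedules.** Part-2 scans are 9-weekly (protocol Table 3) and Part-3 scans 6-weekly (protocol Table 4), each within 7 days either way. Protocol 8.1 has Part-1, Part-4 and Part-3A scanned every 2 cycles to C7D1, then every 3 cycles.

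**The concern.** The DoR sentence is the formal endpoint definition, and it departs from every other statement of that endpoint without being declared as a change. The two table problems are of the same kind: a participant's data satisfy two instructions that give different answers. In an open-label study with cohorts of 20 or 40, one reclassified death can visibly move a Kaplan-Meier curve, and a choice between conflicting rules should not be left until the data are known. DoR is secondary in every part. PFS is secondary in Part-2 and Part-3B.

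**Working it through.** **1. DoR end event, source by source**

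| Source | Deaths that end DoR |
|---|---|
| SAP 4.4, definition | Due to progression only |
| SAP Table 7 | Any |
| SAP Table 2 (Part-2, Part-3B) | Any |
| Protocol 9.4.2 | Any |
| Protocol Table 12 (Part-2, Part-3B) | Any |

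The documents give no death rates, so let q be an assumed share of DoR events that are non-progression deaths. With exponential hazards and a constant share, censoring those deaths multiplies the hazard by 1 − q. The curve S becomes S^(1 − q) and the median is multiplied by 1/(1 − q).

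- q = 5%: 0.5^0.95 = 0.518; median × 1/0.95 = 1.053.
- q = 10%: 0.5^0.90 = 0.536; median × 1/0.90 = 1.111.

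For scale, protocol Table 18 illustrates 4 to 12 responders in a cohort of 20. Even with 12 DoR events, q = 5% is 12 × 0.05 = 0.6 of a death. Within one cohort the matter turns on a single death or none.

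**2. Table 8, death before the first evaluable scan**

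Let k of N participants die before the first scan, with no other early events (k is assumed). PFS at the first scan is (N − k)/N if the deaths are events, and 100% if they are censored at first dose.

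- N = 20: 19/20 = 95% (k = 1); 18/20 = 90% (k = 2).
- N = 40: 39/40 = 97.5% (k = 1); 38/40 = 95% (k = 2).

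With p = k/N, censoring inflates later estimates by 1/(1 − p). A true 50% becomes 0.5/0.975 = 51.3% (1 of 40), 0.5/0.95 = 52.6% (1 of 20 or 2 of 40) or 0.5/0.90 = 55.6% (2 of 20). The performance-status requirement (ECOG 0-1) and the exclusion of predicted life expectancy of 3 months or less point to the low end.

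**3. The 19-week gap**

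The SAP shows no derivation. Two intervals plus one 7-day window reproduces it for Part-2: 2 × 9 + 1 = 19. On 6-weekly scans the same formula gives 2 × 6 + 1 = 13, while 3 × 6 + 1 = 19. The conflict can also be shown without any assumed formula. Progression found at the first scan after m missed scans falls nominally at (m + 1) × interval:

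| Interval | Missed | Week | Row label | Footnote (more than 19 weeks) |
|---|---|---|---|---|
| 9 weeks | 1 | 18 | Event | Event |
| 9 weeks | 2 | 27 | Censor | Censor |
| 6 weeks | 1 | 12 | Event | Event |
| 6 weeks | 2 | 18 | Censor | **Event** |
| 6 weeks | 3 | 24 | Censor | Censor |

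The mismatch affects PFS and DoR in Part-3B. It also affects DoR wherever else scans are 6-weekly: Part-1, Part-4 and Part-3A up to C7D1.

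**4. Schedule inputs**

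Protocol 8.1 gives Part-2 imaging as every 9 weeks but puts 56 days beside it; 9 × 7 = 63, and 56/7 = 8 weeks. An 8-week interval would give 2 × 8 + 1 = 17, so 19 fits the 9-week reading. For Part-3A, two 21-day cycles are 6 weeks, so protocol 8.1 and Table 4 agree up to C7D1. After that, 8.1 moves to three cycles (9 weeks) while Table 4 stays at 6.

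**The case against.** The best defence on DoR is that SAP 4.4 sends the programmer to Table 7, which counts the death, so the analysis will probably be run correctly. That lowers the risk. It does not settle the conflict, because nothing says the table overrides the definition.

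On the gap, footnote a is attached to the row label and can be read as its working definition. A generous gap on 6-weekly scans keeps events rather than discarding them, so this item does not flatter the drug. That stands as to direction. The label and the reported censoring reason would still misdescribe what was done in Part-3B.

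On Table 8, the no-baseline case should be nearly empty, because inclusion criterion I 04 requires measurable disease. That is accepted; the live case is a death with no evaluable post-baseline scan.

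The effects are also small beside the imprecision of 20 to 40 participants, and the study has no formal tests. That stands in full and limits the weight of the point.

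**Conclusion.** The DoR definition is wrong as written, and the Table 8 overlap and the label-to-footnote mismatch are real. If non-progression deaths were censored, median DoR would lengthen by about 5% to 11% for an assumed 5% to 10% share of events. Censoring early deaths at first dose would raise a true 50% PFS to between 51.3% and 55.6% for an assumed 2.5% to 10% of participants. These sizes rest on assumed death rates.

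A reader might infer more than the documents support, in three ways.

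- *That SAP 4.4 actively censors non-progression deaths.* It says participants who "have discontinued from the study, or who have initiated subsequent anticancer therapy will be censored at the last adequate tumor assessment". The protocol lists death under 7.2, "A participant may be withdrawn from the study for any of the following reasons", and under 7.1.1, "A participant must be discontinued from protocol prescribed therapy and removed from the study if any of the following apply". The inference fails because the same censoring sentence follows the any-cause definitions in protocol 9.4.2 and the any-cause PFS definition in SAP 4.4. If leaving the study included dying, those definitions would cancel themselves. Under the DoR sentence such a death is undefined, and Table 7 would count it.
- *That 13 weeks is the correct gap for 6-weekly scans.* That figure rests on an inferred formula with one scan window. With an early scan, one missed scan and a late scan, the span is 84 + 14 = 98 days, or 14 weeks. The same reasoning on 9-weekly scans gives 18 + 2 = 20 weeks, so 19 weeks is not exact in Part-2 either.
- *That the primary result is at risk.* ORR does not use these rules.

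**What to change.** - **SAP 4.4, DoR:** replace the restricted cause of death with death due to any cause.
- **SAP Table 8:** state that a participant without an evaluable post-baseline scan who dies within the missed-assessment window, before any further anticancer therapy, is an event at the date of death. Otherwise censor at first dose. Say whether the window starts at the baseline scan or at first dose, since protocol 8.1 allows Part-2 baseline imaging up to 28 days before C1D1.
- **Tables 7 and 8, footnote a:** make label and gap agree by each part's schedule, including schedules that move from 6-weekly to 9-weekly. Either count scheduled assessments missed, or use two current scan intervals plus a stated window allowance. About 13 to 14 weeks for 6-weekly scans is illustrative only. If 19 weeks is kept there, relabel the row.
- **Protocol 8.1:** reconcile the Part-2 interval in weeks and days with Table 3, and the Part-3A schedule after C7D1 with Table 4.

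The cost is a few words of SAP text before database lock and a short protocol clarification. Reported DoR and PFS may be slightly less favourable, and a shorter gap adds some censoring on 6-weekly scans.

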**Table 7 - DoR analysis - Event and censoring rules**

Situation	Date of outcome	Outcome	Category
Ongoing and no documented progression	Date of the last evaluable tumor assessment documenting no progression	Censored	Ongoing without progression
Documented progression (or Death) at or between scheduled visits	Date of progression (or Date of death)	Event	Documented progression (or Death without documented progression)
Documented progression (or Death) occurring after two or more non-evaluable tumor assessment a	Date of the last evaluable tumor assessment documenting no progression	Censored	Event occurred after two or more missed tumor assessment
Initiation of further anti-cancer therapy	Date of the last evaluable tumor assessment before start date of further anti-cancer therapy	Censored	Initiation of further anti-cancer therapy

a An event occurring at least 19 weeks (excluded) after the last evaluable tumor assessment

Progression Free Survival (PFS) per RECIST v1.1 is defined as the time from the date of the first IMP administration of to the first documentation of definitive disease progression or death due to any cause, whichever occurs first. Participants who are still alive and free from progression at the time of data cutoff date, are lost to follow-up, have discontinued from the study, or who have initiated subsequent anticancer therapy will be censored at the last adequate tumor assessment. The detailed censoring rules are listed in the [Table 8](#) below. PFS will be analyzed using Kaplan-Meier methods and following estimates will be provided:

- Kaplan-Meier estimates of the 25th, 50th and 75th percentiles and their associated 90% CIs will be provided. The 90% CIs will be constructed using a log-log transformation of the survival function and the methods of Brookmeyer and Crowley.
- Number of patients at risk as well as the probabilities of being event-free at least 2, 4, 6, 8, 10 and 12 months with 90% CIs will be estimated using the Kaplan-Meier method and a log-log approach based on a normal approximation following the Greenwood's formula.
- Kaplan-Meier curves will be plotted. These plots will include the number of patients at risk at key time points.

In addition, number (%) of events and patients censored will be presented with type of events and reason of censoring.

[figure not shown]
